### **14.5 ROLE OF STUDY SPONSOR**

The study will be sponsored by Imperial College London (Imperial) with responsibilities defined by a written agreement.

## 15 PUBLICATION

The results from different centres will be analysed together and published as soon as possible after the end of the study. Individual clinicians must not publish data concerning their participants that are directly relevant to questions posed by the study until the PMG has published its report. The PMG together with the RIVER collaborators will form the basis of the writing committee and decide on the nature of publications. Any release, of efficacy or safety data, presentation or publication will be agreed with the TSC according to the terms of their charter.

All publications will acknowledge the participating centres and clinicians, and these will be detailed in an appendix to the main report. Papers will have named authors determined by the PMG according to the following principles:

- To be as inclusive as possible where this is practicable
- To ensure that there is justification for anyone to be named as an author
- Reasons for nomination for authorship may include: study design; grant holding; day-to-day study oversight (PMG membership); analysis; discussion and interpretation of data; representation for key groups; active participation at large recruiting sites. It should be accepted that the people qualifying for authorship will vary over time. In addition, key positions will vary depending on the nature of the publication: clinical lead for clinical papers, statistician lead for methodology papers, translational papers may be led by authors not on the main PMG if appropriate. In the event of any dispute related to authorship or data release, the TSC will be responsible for making the executive decision.

In the manuscript, a full list of sites and the number of participants recruited will be provided. In the presentations, this list of sites will also be shown. The term “the RIVER investigators” will clearly be stated and relevant names included in the presentation credits.

## 16 PROTOCOL AMENDMENTS

Protocol v1.0 24-Oct-2014 approved by REC 23-Dec-2014 and MHRA 13-Jan-2015	
Protocol v2.0 03-Jun-2015 approved by REC 25-Jun-2015. Not accepted by MHRA.	
Changes made	Sections updated
Schedule amended to allow for repeat testing of a participant's viral load, until this falls below the level of detectability. Trial assessment schedule has been split into two stages, pre and post-randomisation, with randomisation becoming a separate visit to ensure all participants have a common baseline. All visits after randomisation are now referred to as post-randomisation weeks (PR week), which has been updated throughout.	Table 1 – Trial Assessment Schedule Table 2 – Visit names and codes Figure 1 Trial Entry, Randomisation and Treatment 3.2 Criteria for Randomisation 3.3 Number of participants 4. Screening, Enrolment & Randomisation
Eligibility assessments including routine blood results and resting 12-lead ECG need to be within 14 days of randomisation.	Table 1 – Trial Assessment Schedule 3.2 Criteria for Randomisation
Wording clarified for enrolment exclusion criteria 22.	3.1.2 Enrolment Exclusion Criteria
Removed the requirement for participants to attend visits fasted.	Table 1 – Trial Assessment Schedule 6.1.1 Screening and Enrolment (Week 0)
Changes to the trial assessment schedule only: 
 
▪ Screening/baseline visit is now referred to as screening only.
 
▪ Follow up visit at week 08 has been removed
 
▪ For several visits the volumes and timings of blood samples have been changed. Total blood volume taken across the protocol has increased by 17ml.
 
▪ Visits where quality of life questionnaires are required have changed.
 
	Table 1 – Trial Assessment Schedule
Further clarification on the vaccination visits has been included: 
 
▪ Specified that the first vaccination (Chad) at PR week 00 must take place within 1 week of randomisation. For participants in Arm A, this visit can be completed over the phone.
 
▪ There is a window of 7 days between the two vaccinations given at PR week 00 and PR08 Day 1.
 
	Table 1 – Trial Assessment Schedule 5.3 Post-Randomisation (PR) Treatment 5.5.3 Vaccines

 
▪ Preliminary results from the BCN01 study are now available.
 
▪ Results from the START study are now available
 
	1.2.5.C Use of ChAdV63.HIVconv and MVA.HIVconv in HIV Infection 11.2.1 Ethical Considerations
Event reporting section has been updated : 
 
▪ Only grade 3 adverse events are reportable prior to randomisation. Grade 4 events are reportable throughout the study as SAEs.
 
▪ Pregnancy in a partner is now considered a notable event
 
	7.3 Other Notable Events 7.3.1 Vaccine related events 7.4 Investigator Responsibilities 7.4.2 Notification Procedure

 
▪ Vaccine related events have been added to the notable events and are listed in Appendix IV.
 
▪ For SAEs, participants must be identified by study number, 3 letter code and year of birth only.
 
▪ Clarification that HERVs may be investigated as an exploratory outcome.
 
	

 
▪ Re-clarification of the end of the interventional phase of the study and end of study.
 
	7.4.1.E Notification 11.1 Compliance

Change in staff at the RIVER Co-ordinating Centre and PI at Brighton and Sussex University Hospitals NHS Trust.
 
Protocol version number and date updated on first page and on all page headers.
	

Protocol v3.0 23-Jul-2015 approved by REC 29-Jul-2015 and MHRA 25-Aug-2015
	
Changes made	Sections updated
Re-clarification of the investigator's event reporting responsibilities.	7.4.1.E Notification

Protocol version number and date updated on first page and on all page headers.
	

Protocol v4.0 18-May-2016 approved by REC 16-Jun-2016 and MHRA 22-Jun-2016
	
Changes made	Sections updated
Additional QTc information Change of QTc and bradycardia eligibility criteria	1.1.1.A Pharmacokinetics (PK) 3.1.2 Enrolment Exclusion Criteria 3.2 Criteria for Randomisation 5.4 Criteria for Starting Vorinostat
Trial Assessment Schedule only: 
 
▪ Additional ECGs at PR10-1 and PR16 included
 
	Table 1 – Trial Assessment Schedule
Eligibility has been updated to: 
 
▪ Enable sites to use either Hepatitis C RNA or Hepatitis C antigen test to exclude current infection.
 
▪ Enforce use of the CKD-EPI equation to calculate eGFR.
 
	3.1.2 Enrolment Exclusion Criteria 3.2 Criteria for Randomisation 5.4 Criteria for Starting Vorinostat
Clarification on use of ART prior to enrolment	1.3 Study Design and Hypothesis 3.1.1 Inclusion Criteria 5.2 Pre-Randomisation Treatment
Removed requirement for participants to return empty/part used Raltegravir	5.5.2 Raltegravir
Removal co-enrolment in UK Register of HIV seroconverters	3.3 Number of participants 4.3 Co-enrolment Guidelines 6.5 Early Stopping of Follow-up

Protocol version number and date updated on first page and on all page headers.
	

Protocol v5.0 20-Oct-2016
	
Changes made	Sections updated
Addition of Cohort II – Previously diagnosed participants	Summary of Trial Trial Schema Figure 1 Trial Entry, Randomisation and Treatment – Cohort I - Recently diagnosed Figure 2 Trial Entry, Randomisation and Treatment – Cohort II - Previously diagnosed Table 1 Trial Assessment Schedule – Cohort I - Recently

	
diagnosed
 
Table 2 Trial Assessment Schedule – Cohort II - Previously diagnosed
 
Table 3 Visit names and codes – Cohort I - Recently diagnosed
 
Table 4 Visit names and codes – Cohort II – Previously diagnosed
 
1.3 Study Design and Hypothesis
 
3 Selection of Participants
 
4 Enrolment & Randomisation
 
5 Treatment of Participants
 
Figure 5 RIVER Treatment Schedule – Cohort I – Recently diagnosed
 
Figure 6 RIVER Treatment Schedule – Cohort II – Previously diagnosed
 
7.2.1 Large volume blood draw
 
7.4 Investigator Responsibilities
 
7.4.1.E Notification
 
9 Statistical Considerations

Additional 18ml blood sample for Merck assay at PR11-1	
Table 1 Trial Assessment Schedule – Cohort I - Recently diagnosed
 
Table 2 Trial Assessment Schedule – Cohort II - Previously diagnosed

Change of eGFR eligibility criteria	
3.3.1 Enrolment Inclusion Criteria
 
3.3.3 Criteria for Randomisation
 
3.4.2 Randomisation Exclusion Criteria
 
5.5 Criteria for Starting Vorinostat

References to TMG updated to PMG	
2.1 Site/Investigator Inclusion Criteria
 
9.4 Interim Monitoring & Analyses
 
14 Oversight & Trial Committees
 
15 Publication

Protocol version number and date updated on first page and on all page headers.	

### Revision History

Version	Author	Date	Reason for Revision
0.1	[name], [name]	24-Oct-2014	As in protocol version 1.0
0.2	[name]	09-Mar-2017	Initial full draft
0.3	[name]	16-Mar-2017	Reviewed by [name]
0.4	[name]	20-Jul-2017	Reviewed by [name], [name], [name], [name], [name]
1.0	[name]	04-Dec-2017	Final version, after further review by [name], [name], [name], [name], [name], [name]. Major changes: - Primary Endpoint: Clarifying handling of undetectable and missing values - Viral Outgrowth: Clarifying analysis method - HIV-specific T cell responses: Changed method from Elispot to ICS

## 1 OVERVIEW OF RIVER

### 1.1 SUMMARY

[figure not shown]
TRIAL NAME	RIVER (RESEARCH IN VIRAL ERADICATION OF HIV RESERVOIRS)
Interventions to be compared	
This study is a two-arm prospective randomised controlled trial comparing:
 
Arm A: 4-drug cART including raltegravir (control)
 
Arm B: 4-drug cART including raltegravir plus ChAdV63.HIVconsv prime and MVA.HIVconsv boost vaccines; followed by a 28-day course of vorinostat (10 doses in total).

Study Hypothesis	In primary HIV infection, a combination of immediate cART, immunisation and latency reactivation using the HDACi vorinostat will confer a significant reduction in the reservoir when compared with cART alone.
Participants	
The study aims to enrol 60 individuals across 6 UK collaborating clinical centres, from two different strata:
 
Stratum I: Recently diagnosed with primary HIV-1 infection [see protocol for definition]. Participants must be enrolled within 4 weeks of a confirmed diagnosis of primary HIV-1 infection. Eligible participants are enrolled at week 0 when combination ART (cART) begins. Randomisation of participants occurs after assessment of eligibility at week 22.
 
Stratum II: Previously diagnosed with primary HIV-1 infection. Confirmed diagnosis of primary HIV-1 infection must be within a maximum of 2 years prior to randomisation. Participants must have started at least 3-drug ART within 4 weeks of a confirmed diagnosis of primary HIV-1 infection and remained on ART since starting. Randomisation of participants occurs within 2 weeks of the assessment of eligibility at screening.

Randomisation	The participants enrolled in the trial are randomised in a 1:1 ratio to one of two intervention arms, with randomisation stratified by the two strata defined above.

## 1.2 TRIAL SCHEMA

### Stratum I - Recently diagnosed

### Stratum II - Previously diagnosed

## 1.3 OUTCOME MEASURES

### 1.3.1 PRIMARY OUTCOME MEASURE

The primary outcome measure is total HIV DNA from CD4 T-cells averaged across post-randomisation weeks 16 and 18.

### 1.3.2 SECONDARY OUTCOME MEASURES

- Clinical and laboratory adverse events, all grades, including SAE
- Further assessment of the HIV reservoir e.g. HIV integrated DNA; HIV cell associated RNA; plasma HIV RNA measured with an ultra-low copy assay i.e. with a threshold of <1 copy/ml, viral outgrowth assays
- Studies of immune function including measuring the latently-infected resting memory T-cells and HIV-specific T cell responses (in protocol vs 5.0: cytotoxic immune responses)
- Changes in inflammatory biomarkers

## 1.4 SAMPLE SIZE

The sample size calculation is based on the primary endpoint which will be analysed on a  $\log_{10}$ -scale. The following assumptions are made:

- The combination intervention will confer a 50% reduction in total HIV DNA when compared with cART alone. On a  $\log_{10}$ -scale this corresponds to a difference between the two arms of  $\log_{10}(2)$  (approximately 0.3). The effect is assumed to be the same in both strata (recently and previously diagnosed patients).
- Standard deviation (SD) is 0.4 for a single measurement in both arms based on two publications:
  - Reported on data from 31 participants treated with HAART at PHI in the French PRIMO study. The median (IQR) at 6 and 12 months after starting treatment were 2.30 (2.10, 2.70) and 2.10 (1.80, 2.40)  $\log_{10}$  DNA copies/ $10^6$  PBMC respectively suggesting a SD of 0.45 at both time points.
  - Reported on 8 participants with PHI. At week 52, the median (IQR) was 494 (250 - 694) for total HIV-1 DNA copies/ $10^6$  CD4+ T-cells suggesting a SD (in log scale) of 0.33.
- 1:1 allocation of participants in the two study arms.
- Method of analysis: comparing the treatment arms in terms of absolute HIV total DNA level at post-randomisation weeks 16 and 18 adjusted for baseline (here: randomisation) level (analysis of covariance; ANCOVA); one baseline measurement and two follow-up measurements (at PR16 and 18) will be taken for an individual participant.
- A correlation coefficient of 0.5 between a baseline measurement and a PR 16/18 measurement, and a correlation coefficient of 0.7 for measurements at PR 16 and 18.
- Two-sided  $\alpha = 0.05$  for the null hypothesis that there is no difference between the two arms in the primary endpoint.

Under the above assumptions, a sample size of 52 individuals would provide 94% power to detect a 50% reduction in HIV total DNA (86% power for a 45% reduction).

Assuming that some individuals enrolled will not reach visits PR 16/18 (due to failing the eligibility criteria for randomisation in stratum I, or withdrawal) it is planned to enrol a total of 60 individuals overall (both strata combined).

## 2 DEFINITIONS

### 2.1 DEFINITION OF BASELINE

Baseline is defined in this trial as the time of randomisation. Baseline values used to define changes in immunological, virological and other measurements over time for each participant are defined as the measurements at randomisation. If a measurement at randomisation is not available, then the measurement at week 22 (stratum I) or screening (stratum II) closest to randomisation (but within 14 days before) will be used. If no measurement is available at or prior to randomisation then any measurement taken up to 7 days post-randomisation will be used providing this is before the start of vaccination.

### 2.2 DEFINITION OF UNDETECTABLE HIV-RNA

Undetectable plasma HIV RNA is defined <200 copies/mL for the Taqman Roche 2.0 assay, and as <50 copies/mL for all other assays.

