## 6.2 PROCEDURES FOR ASSESSING EFFICACY

The efficacy of cART will be determined using viral load assays obtained at the local laboratories. In particular participants must have a plasma HIV RNA <50 copies/mL (<200 copies/mL if Taqman 2.0 Roche testing platform used) to be eligible for randomisation, either at week 22 (or any necessary repeat visits) or – for Cohort II – at screening. Any evidence of viral rebound during the study must be managed in accordance with standard national treatment guidelines.

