#### 9.2.2 SECONDARY OUTCOME MEASURES

Secondary outcome measures include

- Clinical and laboratory adverse events
- Further assessment of the HIV reservoir e.g. HIV integrated DNA; HIV cell associated RNA; plasma HIV RNA measured with an ultra-low copy assay i.e. with a threshold of <1 copy/ml and viral outgrowth assays.
- Studies of immune function including measuring the latently-infected resting memory T-cells and cytotoxic immune responses
- Changes in inflammatory biomarkers

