### 4.3 PATIENT CHARACTERISTICS

The following baseline characteristics will be presented overall and by randomised group. For the grouping of quantitative variables, categories will be chosen after univariate inspection of the data, ensuring that a reasonable number of participants are represented in each category.

Before completion of randomisation, the same characteristics will also be reported for all patients enrolled but not by randomised group.

- Stratum: number (%) stratum I, stratum II
- Age: median (IQR), range; distribution in categories
- Sex: number (%) male, female
- Ethnicity: number (%) White, South Asian, South East Asian, Hispanic/Latino, Black African, Black Caribbean/American, mixed ethnic group, other
- Mode of HIV infection: number (%) sex between men, sex between men and women, injection drug use, blood products, unknown, other
- CD4 count (current): median (IQR), range; distribution into categories
- HIV-RNA: number (%) undetectable; distribution into categories
- Criteria for PHI diagnosis: number (%) positive HIV-1 serology, positive p24, HIV RNA or proviral DNA, 4th generation HIV test, western blot, RITA only.
- eGFR: median (IQR), range
- QTc interval: median (IQR), range
- Haematology/biochemistry/electrolytes/glucose/lipids/urine analysis: median (IQR), range of test results

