## 4.6 PRIMARY ENDPOINT

The primary outcome measure is based on total HIV DNA from CD4 T-cells (copies/million CD4+T cells) which is measured at enrolment (in recently infected patients), baseline, PR week 08-3, PR week 12-2, PR week 16, and PR week 18.

The primary endpoint is total HIV DNA averaged across post-randomisation weeks 16 and 18. It will be analysed on a  $\log_{10}$ -scale. Treatment arms will be compared in terms of absolute total HIV DNA levels at post-randomisation weeks 16 and 18 adjusted for the baseline (i.e. randomisation) level and by stratum using analysis of covariance.

Each sample of a particular time-point is measured in triplicates. Any result below the lower detection limit (LDL) - including undetectable DNA but NOT missing values - will be replaced by LDL/2. A value of 5 HIV copies/well will be adopted as lower limit of detection.

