## 4.7 SECONDARY ENDPOINTS: EFFICACY

- HIV integrated DNA:**

Measurements (copies/million CD4+T cells) at enrolment (in recently infected patients), baseline, PR week 08-3, PR week 12-2, PR week 16, and PR week 18.

Analysed as for continuous outcomes as specified above. Treatment arms will be compared in terms of absolute integrated HIV DNA levels at post-randomisation weeks 16 and 18 adjusted for the baseline level and by stratum.

- Plasma HIV RNA measured with an ultra-low copy assay:**

Number (%) with undetectable HIV-RNA at enrolment (in recently infected patients), baseline, PR week 08-3, PR week 09-2, PR week 12-2, PR week 16, and PR week 18; analysed as for binary outcomes as specified above.

- **Replication competence (Viral Outgrowth assay):**

Measurements (infectious units per million cells; IUPM) at baseline and PR week 16. Analysed as for binary and continuous outcomes as specified above. The results are expected to be “negative” (i.e. below the lower limit of detection) in a sizable proportion of samples. Therefore, the treatment arms will be compared as follows:

- 1) Primary analysis:
  - a) Comparison of the proportion of patients with a “negative” result using logistic regression. This analysis includes all patients with a valid PR-16 result.
  - b) Comparison of IUPM in patients with “positive” results using median regression. Patients with a “negative” PR-16 result will be excluded.
- 2) Secondary analysis:  
Comparison of IUPM using a linear model appropriate for left-censored data. This analysis includes all patients with a valid PR-16 result, “positive” or “negative”.

In all analyses, patients with missing PR-16 samples or invalid PR-16 results (due to assay failure) will be ignored. Analyses will be adjusted for stratum and baseline viral outgrowth. Missing baseline values will be imputed; predictors may include stratum, and other factors associated eg CD4, HIV-DNA.

- **HIV-specific T cell responses (both CD8+ and CD4+ T cell responses):**

Measurements using intracellular cytokine staining (ICS) at enrolment (in recently infected patients), baseline, PR week 09-2, PR week 12-2, and PR week 16. For both CD8+ and CD4+ T cells, the following markers will be measured: CD107a+, CD154+, IFNg+, IL2+, and TNFa+.

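### Does the SAP's general 50 copies/mL definition of undetectable HIV RNA govern the ultra-low copy assay?

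*SAP*

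**What the plan says.** SAP 2.2 gives one definition for the term: "Undetectable plasma HIV RNA is defined <200 copies/mL for the Taqman Roche 2.0 assay, and as <50 copies/mL for all other assays". It names no exception and does not say that it covers only routine viral-load tests.

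SAP 4.7 has an entry for plasma HIV RNA by ultra-low copy assay. Its measure is "Number (%) with undetectable HIV-RNA at enrolment (in recently infected patients), baseline, PR week 08-3, PR week 09-2, PR week 12-2, PR week 16", followed by PR week 18, analysed as a binary outcome. That entry gives no limit.

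The limit appears where the outcome is defined. SAP 1.3.2 lists "plasma HIV RNA measured with an ultra-low copy assay i.e. with a threshold of <1 copy/ml". Protocol 9.2.2 has "plasma HIV RNA measured with an ultra-low copy assay i.e. with a threshold of <1 copy/ml and viral outgrowth assays", and the Summary of Trial gives the same threshold.

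Two other uses of viral load matter here. SAP 4.3 asks for a baseline description: "HIV-RNA: number (%) undetectable; distribution into categories". SAP 4.9 asks for the number and percentage with suppressed HIV RNA at scheduled visits.

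**The concern.** SAP 4.7 uses the very term that SAP 2.2 defines, and 2.2 covers every assay other than one named platform. A programmer working only from those two sections could code the ultra-low copy result as undetectable whenever it is under 50 copies/mL.

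That would empty the endpoint. Protocol 3.3.3 and 3.4.1 require HIV RNA under 50 copies/mL (under 200 on Taqman Roche 2.0), assessed within 14 days before randomisation. With the same cut-off, nearly all participants would be undetectable at baseline in both arms, and would stay so while suppression held. The measure would come close to repeating the suppression summary in SAP 4.9. The tests and models for binary outcomes in SAP 3 would have almost no variation to work with.

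Other parts of the SAP are more explicit about limits. For total HIV DNA, SAP 4.6 says "A value of 5 HIV copies/well will be adopted as lower limit of detection" and substitutes half the limit. For viral outgrowth, SAP 4.7 defines a negative result ("i.e. below the lower limit of detection) in a sizable proportion of samples").

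**Working it through.** The question is the scope of a definition, so the main check sets the texts side by side.

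| Place | Subject | Limit |
|---|---|---|
| SAP 2.2 | plasma HIV RNA, general | <200 (Taqman Roche 2.0), <50 (other assays) copies/mL |
| Protocol 3.3.3, 3.4.1 | eligibility for randomisation | same pair |
| Protocol 6.2 | viral load from local laboratories | same pair |
| SAP 1.3.2; Protocol 9.2.2; protocol summary | ultra-low copy assay, by name | <1 copy/mL |
| SAP 4.7 | ultra-low copy assay, by name | none repeated |

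**Step 1: where the limits in 2.2 come from.** The 200/50 pair, with the same platform named, is the eligibility rule. Protocol 6.2 places it with routine testing: "The efficacy of cART will be determined using viral load assays obtained at the local laboratories". In that setting the other assays are the other routine platforms. So limited, 2.2 still has work to do: it serves the baseline item in SAP 4.3 and is the natural basis for the suppression summary in 4.9.

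**Step 2: which limit belongs to the 4.7 entry.** The entry carries the same outcome name as SAP 1.3.2, where the threshold is part of the description. A number written for a named assay takes precedence over a general one. The opposite reading would run a sensitive assay and then discard its sensitivity.

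**Step 3: what the literal reading would do.** Ratio of cut-offs: 50 / 1 = 50. For illustration only, suppose log10 HIV RNA on treatment is normal with median m copies/mL and SD s. The share below a cut-off c is Φ((log10 c − log10 m)/s). The documents give neither m nor s; the values below are assumptions.

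- m = 0.5, s = 0.5: below 1, Φ(0.301/0.5) = 73%; below 50, Φ(2.000/0.5) = 100%.
- m = 5, s = 0.5: below 1, Φ(−0.699/0.5) = 8%; below 50, Φ(1.000/0.5) = 98%.
- m = 5, s = 0.7: below 1, Φ(−0.699/0.7) = 16%; below 50, Φ(1.000/0.7) = 92%.

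Over m from 0.5 to 5 and s from 0.5 to 0.7, 92% to 100% fall below 50 copies/mL, against 8% to 73% below 1 copy/mL. An analyst who applied the wrong cut-off would see an endpoint close to 100% in both arms, which would itself prompt a check against SAP 1.3.2.

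**Step 4: PR09-2.** SAP 4.7 lists seven visits for this assay, five of them after randomisation. In Table 1 (Cohort I) the row that includes low-copy viral load has six entries of 60 or 80 ml: enrolment, randomisation, PR08-3, PR12-2, PR16 and PR18. They match the other six visits. The row's 18 ml entry fits the sample added at PR11-1 in protocol version 5.0. The PR09-2 total is 86 ml = 14 (routine) + 32 (immunology) + 40 (vorinostat virology, arm B only), which leaves 86 − 86 = 0 for the low-copy row. However, the 32 ml immunology draw is not restricted to arm B and goes to the same centre (Oxford), so it could supply plasma. Table 2 (Cohort II) was not in the text available. The mismatch is therefore open. If no sample exists at that visit, SAP 3 analyses secondary endpoints on available data, and the visit has nothing to contribute.

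**The case for a change.** The strongest case for amending the SAP is that it has no rule on which definition prevails, that 2.2 is worded to cover every other assay, and that 4.7 is the only outcome analysis using exactly the defined term. The trial is open label, so a cut-off left to inference is a choice made by people who may know the allocation. The revision history shows that version 1.0 clarified undetectable values for the primary endpoint and the analysis method for viral outgrowth, but not this assay. There is also no rule for a sample that cannot be read down to 1 copy/mL, and the draw is 60 ml at one visit and 80 ml at the others.

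The observation about wording stands: neither section refers to the other. The rest carries little weight.

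- **Discretion.** The threshold of 1 copy/mL is in the protocol dated 20-Oct-2016 and again in the SAP finalised on 04-Dec-2017. Using it applies what is written and is not a choice made after seeing data.
- **Contrast with other assays.** The outgrowth entry refers to a lower limit of detection without giving a number. The ultra-low copy assay has one. Only total DNA is specified more fully.
- **Varying limit.** The 60 and 80 ml volumes are shared by total and integrated DNA, cell-associated RNA, genomics, low-copy viral load and p24. The documents do not give the plasma volume used for the low-copy test, or say that any sample would miss 1 copy/mL. A rule for undetermined results would rest on an assumption.
- **Duplication of SAP 4.9.** This follows only if the literal reading is adopted.

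**Conclusion.** No change follows. There is a literal gap in scope between SAP 2.2 and 4.7, but SAP 1.3.2 and Protocol 9.2.2 fill it with a number for this very outcome, and the context of 2.2 confines it to routine viral load. A cross-reference would be tidier, but it would not alter any result that a competent analyst would produce.

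The size is one secondary reservoir measure and a 50-fold difference between two cut-offs, of which only the lower is plausible for this assay. No effect or power figure can be given, because the documents report no detection rates. The primary endpoint, sample size and safety analyses are unaffected.

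This rests on two judgements: that an assay-specific threshold overrides a general definition, and that analysts read the outcome list together with the analysis section. The source of the PR09-2 sample remains a query for the laboratory and does not bear on the conclusion.
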